#### 11.1.2 Serious Adverse Event (SAE)

A SAE is an adverse event that:

- Results in death. **NOTE:** Death due to disease progression should not be reported as a SAE, unless it is attributable by the site investigator to the study drug(s)
- Is life-threatening (defined as an event in which the subject was at risk of death at the time of the event; it does not refer to an event which hypothetically might have caused death if it were more severe)
- Requires inpatient hospitalization for >24 hours or prolongation of existing hospitalization. **NOTE:** Hospitalization for anticipated or protocol specified procedures such as administration of chemotherapy, central line insertion, metastasis interventional therapy, resection of primary tumor, or elective surgery, will not be considered serious adverse events.
- Results in persistent or significant disability/incapacity
- Is a congenital anomaly or birth defect
- Is an important medical event (defined as a medical event(s) that may not be immediately life-threatening or result in death or hospitalization but, based upon appropriate medical and scientific judgment, may jeopardize the subject or may require intervention (e.g., medical, surgical) to prevent one of the other serious outcomes listed in the definition above). Examples of such events include, but are not limited to, intensive treatment in an emergency room or at home for allergic bronchospasm; blood dyscrasias or convulsions not resulting in hospitalization; or the development of drug dependency or drug abuse.

### 11.1.3 Unexpected Adverse Event

For this study, an AE is considered unexpected when it varies in nature, intensity or frequency from information provided in the current IB, prescribing information or when it is not included in the informed consent document as a potential risk. Unexpected also refers to AEs that are mentioned in the IB as occurring with a class of drugs or are anticipated from the pharmacological properties of the drug, but are not specifically mentioned as occurring with the particular drug under investigation.

### 11.1.4 Relatedness

AEs will be categorized according to the likelihood that they are related to the study drug(s). Specifically, they will be categorized using the following terms:

Unrelated	Adverse Event is not related to the study drug(s)
Unlikely	Adverse Event is doubtfully related to the study drug(s)
Possible	Adverse Event may be related to the study drug(s)
Probable	Adverse Event is likely related to the study drug(s)
Definite	Adverse Event is clearly related to the study drug(s)

### 11.1.5 Definition and Reporting of a Pembrolizumab and Lenvatinib Overdose

For purposes of this trial, an overdose will be defined as any dose of 1,000 mg or greater ( $\geq 5$  times the indicated dose). No specific information is available on the treatment of overdose of pembrolizumab or lenvatinib. In the event of overdose, subject should be observed closely for signs of toxicity. Appropriate supportive treatment should be provided if clinically indicated. If an AE (s) is associated with (“results from”) the overdose of pembrolizumab or lenvatinib, the AE(s) is reported as a SAE, even if no other seriousness criteria are met.

If a dose of pembrolizumab or lenvatinib meeting the protocol definition of overdose is taken without any associated clinical symptoms or abnormal laboratory results, the overdose is reported as a non-serious ECI, using the terminology “accidental or intentional overdose without adverse effect.”

All reports of overdose with and without an AE (and other Reportable Events) must be reported on a HCRN Serious Adverse Event Submission Form **within 1 business day** to HCRN safety via email: [[contact]](mailto:[contact]). HCRN will report the event **within 1 business day** to Merck Global Safety (Attn: Worldwide Product Safety; [contact]).

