### **1.3.2 Lenvatinib (Lenvima) Dose Justification**

A variety of doses have been used for the different clinical uses of lenvatinib [7]. The starting dose utilized for single agent lenvatinib was 24 mg once daily in thyroid cancer trials and 12 mg and 8 mg once daily respectively for patients with advanced hepatic cancers with body weight  $>60$  kg and  $< 60$  kg. In renal cancer lenvatinib 18 mg oral daily dose in combination with everolimus 5 mg daily demonstrated improved efficacy and received FDA approval. Keynote 146 was a phase IB/II trial conducted in metastatic endometrial cancer that used a combination of lenvatinib 20 mg oral daily dose and pembrolizumab 200 mg IV every 21 days. The combination received accelerated FDA approval in 2019 and safety is well established in this trial. Since the same combination is being evaluated in the current proposed trial the starting dose of lenvatinib in this trial is 20 mg orally daily.

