#### 1.4.2 Justification for Dose

The planned dose of pembrolizumab for this study is 200 mg every 3 weeks (Q3W). Based on the totality of data generated in the Keytruda development program, 200 mg Q3W is the appropriate dose of pembrolizumab for adults across all indications and regardless of tumor type. As outlined below, this dose is justified by:

- Clinical data from 8 randomized studies in melanoma and NSCLC indications demonstrating flat dose- and exposure-efficacy relationships from 2 mg/kg Q3W to 10 mg/kg Q2W, representing an approximate 5- to 7.5-fold exposure range (refer to IB, Section 5.2.2)

- Population PK analysis showing that both fixed dosing and weight-based dosing provides similar control of PK variability with considerable overlap in the distributions of exposures, supporting suitability of 200 mg Q3W
- Clinical data showing meaningful improvement in benefit-risk including overall survival at 200 mg Q3W across multiple indications, and
- Pharmacology data showing full target saturation in both systemic circulation (inferred from pharmacokinetic [PK] data) and tumor (inferred from physiologically-based PK [PBPK] analysis) at 200 mg Q3W

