## **5.3 Pembrolizumab**

Pembrolizumab 200 mg will be administered as a 30 minute IV infusion every 3 weeks. Sites should make every effort to target infusion timing to be as close to 30 minutes as possible. However, given the variability of infusion pumps from site to site, a window of -5 minutes and +10 minutes is permitted (i.e., infusion time is 30 minutes: -5 min/+10 min).

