### 6.1.1 Dose Levels for Dose Reductions of Lenvatinib

Dose level	Dose of Lenvatinib
Starting Dose	20 mg
Dose level (-1)	14 mg
Dose level (-2)	10 mg
Dose level (-3)	8 mg

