### **11.1.7 Definition and Reporting of Events of Clinical Interest (ECI)**

Selected non-serious and SAEs are also known as ECI and must be recorded as such on the Adverse Event case report forms/worksheets and reported to HCRN **within 1 business day** of the event.

ECI for this trial include:

1. An overdose of pembrolizumab or lenvatinib, as defined above, that is not associated with clinical symptoms or abnormal laboratory results.
2. An elevated AST or ALT lab value that is greater than or equal to  $3 \times$  the upper limit of normal, **and** an elevated total bilirubin lab value that is greater than or equal to  $2 \times$  the upper limit of normal, **and**, at the same time, an alkaline phosphatase lab value that is less than  $2 \times$  the upper limit of normal, as determined by way of protocol-specified laboratory testing or unscheduled laboratory testing. **NOTE:** These criteria are based upon available regulatory guidance documents. The purpose of the criteria is to specify a threshold of abnormal hepatic tests that may require an additional evaluation for an underlying etiology.

ECIs that occur in any subject from the date of first dose through 90 days following cessation of treatment, or 30 days following cessation of treatment if the subject initiates a new anticancer therapy, whichever is earlier, whether or not related to pembrolizumab or lenvatinib, must be reported **within 1 business day** to [[contact]](mailto:[contact]). HCRN will report the event **within 1 business day** to Merck Global Safety (Attn: Worldwide Product Safety; [contact]).

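### The single 1,000 mg overdose threshold is 5 times the pembrolizumab dose but 50 times the lenvatinib dose, so lenvatinib overdoses could go unreported

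*Combined protocol and SAP*

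**What the plan says.** Section 11.1.5 is headed as the overdose definition for pembrolizumab and lenvatinib together. Its definition names neither drug: "an overdose will be defined as any dose of 1,000 mg or greater". A parenthesis glosses this as at least 5 times the indicated dose.

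The planned doses are an order of magnitude apart:

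- Pembrolizumab (Section 5.3): "Pembrolizumab 200 mg will be administered as a 30 minute IV infusion every 3 weeks".
- Lenvatinib (Section 1.3.2): "the starting dose of lenvatinib in this trial is 20 mg orally daily". Section 6.1.1 allows reductions to 14, 10 and 8 mg.

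The definition is then applied to both drugs:

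- Within 11.1.5, an adverse event that results from an overdose of either drug is reported as serious even when no other seriousness criterion is met.
- The symptom-free case is covered by "If a dose of pembrolizumab or lenvatinib meeting the protocol definition of overdose is taken without any associated clinical symptoms or abnormal laboratory results", and is reported as a non-serious event of clinical interest (ECI).
- The first item in the ECI list of Section 11.1.7 is "An overdose of pembrolizumab or lenvatinib, as defined above, that is not associated with clinical symptoms or abnormal laboratory results".

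These reports go to the coordinating organisation within 1 business day and from there to the supplier within a further business day. The documents give no separate overdose threshold for lenvatinib.

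**The concern.** The milligram figure and the multiple are meant to say the same thing, and for lenvatinib they do not. The figure fits the pembrolizumab dose only, yet the heading, the rules in 11.1.5 and the ECI list all extend it to lenvatinib.

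Two safety-reporting steps depend on the definition: the expedited ECI report of a symptom-free overdose, and the automatic upgrade of an overdose-related adverse event to serious. If the milligram figure is followed, neither would be triggered for lenvatinib short of 50 starting doses taken as one.

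Lenvatinib is also the drug for which the definition is more likely to be needed. It is taken by mouth every day and recorded in a patient diary (Section 5.2), whereas pembrolizumab is infused at a fixed dose once per cycle. That accidental or intentional excess is likelier with the oral drug is an inference from the route. The documents give no overdose rates for either drug.

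**Working it through.** **Inputs**

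- Threshold: 1,000 mg (11.1.5)
- Multiple: at least 5 times the indicated dose (11.1.5)
- Pembrolizumab dose: 200 mg (1.4.2, 5.1, 5.3)
- Lenvatinib starting dose: 20 mg daily (1.3.2, 5.1)
- Lenvatinib reduced doses: 14, 10 and 8 mg (6.1.1)
- Cycle length: 21 days (5.1)

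**Step 1. Reproduce the stated figure.** Multiple × dose for pembrolizumab is 5 × 200 = 1,000 mg, and 1,000 / 200 = 5. The figure and the multiple agree.

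**Step 2. Apply the same two formulas to lenvatinib.**

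| Lenvatinib dose | 1,000 mg as a multiple (1,000 / dose) | 5 × dose |
|---|---|---|
| 20 mg (starting) | 50 | 100 mg |
| 14 mg | about 71 | 70 mg |
| 10 mg | 100 | 50 mg |
| 8 mg | 125 | 40 mg |

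The figure and the multiple disagree at every dose level.

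**Step 3. Size of the gap at the starting dose.** The ratio of the two thresholds is 1,000 / 100 = 10. An intake of 100 mg up to just under 1,000 mg, which is 5 to just under 50 times the dose, meets the multiple and misses the milligram figure.

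**Step 4. Can the milligram threshold be reached in practice?** One full cycle of lenvatinib is 21 × 20 = 420 mg. A patient who took a whole cycle's drug at once would still be below 1,000 mg, which corresponds to 1,000 / 20 = 50 days of treatment. How much drug is dispensed at a time is not stated, so this is an illustration of scale.

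**Step 5. Could the definition be meant for pembrolizumab only?** The section heading, the symptom-free rule and the ECI item all name lenvatinib. If the definition were limited to pembrolizumab, lenvatinib would have no overdose definition at all, although both sections rely on one.

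**The case against.** The ratios are not in dispute. The strongest objections concern how far the consequence goes.

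- **The two halves are not strictly incompatible.** A 1,000 mg dose of lenvatinib is also at least 5 times the indicated dose, and a site working from the multiple would report from 100 mg. This is true as logic. But the parenthesis explains the milligram figure, and for lenvatinib it explains it wrongly. Sites that read different halves of the sentence would report different events.
- **Other reporting catches much of it.** Adverse events are recorded whatever their cause (11.2.1). Any event that meets an ordinary seriousness criterion, including important medical events (11.1.2), is reported within 1 business day (11.2.2). Diaries and medication containers are brought to each visit (5.2). This stands and narrows the gap. It does not restore the ECI report for a symptom-free excess of 100 mg to just under 1,000 mg, or the upgrade of a non-serious adverse event that results from one.
- **The 50-fold figure holds only at 20 mg.** This also stands. At reduced doses the mismatch is larger, and the protocol does not say whether the indicated dose is the starting dose or the patient's current dose.
- **Nothing in the efficacy analysis changes.** Agreed. Safety of the combination is, however, a secondary objective.

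**Conclusion.** The concern holds. The overdose threshold in 11.1.5 is correct for pembrolizumab and wrong for lenvatinib by a factor of 10 at the starting dose: 50-fold where the text says 5-fold. The mismatch is wider at the reduced doses.

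The arithmetic rests on the planned doses in the protocol and on reading the definition as covering both drugs, which the wording of 11.1.5 and 11.1.7 requires. The consequence is conditional. Lenvatinib overdoses could go unreported where a site applies the milligram figure, and what is lost is the expedited ECI report and the automatic upgrade to serious.

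The two-stage design, the sample size and the planned analyses are unaffected. The point should be corrected because it concerns the reporting of safety for one of the two study drugs.

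**What to change.** Replace the single definition in 11.1.5 with one for each drug, in which the milligram figure and the multiple agree with the doses in 5.1. Pembrolizumab can keep 1,000 mg. The sponsor and the drug supplier should set the lenvatinib threshold. For reference, the protocol's own 5-times rule gives 100 mg at the 20 mg starting dose. The lenvatinib definition should also say whether it refers to the starting dose or to the dose the patient is currently prescribed, because the rule gives 70, 50 and 40 mg at the reduced levels.

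Section 11.1.7 refers back to 11.1.5 and needs only a check that the cross-reference still reads correctly.

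The cost is a one-sentence protocol clarification, with no effect on sample size or analysis.

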### 11.1.6 Reporting of Pregnancy

Although pregnancy is not considered an adverse event, it is the responsibility of investigators or their designees to report any pregnancy of a participant’s partner (spontaneously reported to them) that occurs from the time of treatment initiation through 120 days following cessation of study drugs. All reported pregnancies must be followed to the completion/termination of the pregnancy. Pregnancy outcomes of spontaneous abortion, missed abortion, benign hydatidiform mole, blighted ovum, fetal death, intrauterine death, miscarriage and stillbirth must be reported as serious events (Important Medical Events). If the pregnancy continues to term, the outcome (health of infant) must also be reported.

All reports of pregnancy with and without an AE must be reported **within 1 business day** to [[contact]](mailto:[contact]) on appropriate Pregnancy Reporting form.. HCRN will report the event **within 1 business day** to Merck Global Safety (Attn: Worldwide Product Safety; [contact]).

### **11.1.7 Definition and Reporting of Events of Clinical Interest (ECI)**

Selected non-serious and SAEs are also known as ECI and must be recorded as such on the Adverse Event case report forms/worksheets and reported to HCRN **within 1 business day** of the event.

ECI for this trial include:

1. An overdose of pembrolizumab or lenvatinib, as defined above, that is not associated with clinical symptoms or abnormal laboratory results.
2. An elevated AST or ALT lab value that is greater than or equal to  $3 \times$  the upper limit of normal, **and** an elevated total bilirubin lab value that is greater than or equal to  $2 \times$  the upper limit of normal, **and**, at the same time, an alkaline phosphatase lab value that is less than  $2 \times$  the upper limit of normal, as determined by way of protocol-specified laboratory testing or unscheduled laboratory testing. **NOTE:** These criteria are based upon available regulatory guidance documents. The purpose of the criteria is to specify a threshold of abnormal hepatic tests that may require an additional evaluation for an underlying etiology.

ECIs that occur in any subject from the date of first dose through 90 days following cessation of treatment, or 30 days following cessation of treatment if the subject initiates a new anticancer therapy, whichever is earlier, whether or not related to pembrolizumab or lenvatinib, must be reported **within 1 business day** to [[contact]](mailto:[contact]). HCRN will report the event **within 1 business day** to Merck Global Safety (Attn: Worldwide Product Safety; [contact]).

## **11.2 Reporting**

### **11.2.1 Adverse Events**

- AEs will be recorded from time of signed informed consent until 30 days after discontinuation of study drug(s) or until a new anti-cancer treatment starts, whichever occurs first.
- AEs will be recorded regardless of whether or not they are considered related to the study drug(s).
- All AEs will be recorded in the subject's medical record and on the appropriate study specific eCRF form within the EDC system.

## 11.2.2 Serious Adverse Events (SAEs)

### 11.2.2.1 Site Requirements for Reporting SAEs to HCRN

- SAEs will be reported from time of signed informed consent until 90 days after discontinuation of study drug(s) or until a new anti-cancer treatment starts, whichever occurs first.
- SAEs will be reported on the SAE Submission Form **within 1 business day** of discovery of the event.
- All SAEs will be recorded in the subject's medical record and on the appropriate study specific eCRF form within the EDC system.

The site will submit the completed SAE Submission Form to HCRN **within 1 business day** of discovery of the event. The form will be submitted to HCRN electronically to [[contact]](mailto:[contact]). The site investigator is responsible for informing the IRB and/or other local regulatory bodies as per local requirements.

The original copy of the SAE Submission Form and the email correspondence must be kept within the study file at the study site.

Once the SAE has resolved, sites must submit a follow-up SAE Submission Form within a reasonable timeframe to HCRN electronically to [[contact]](mailto:[contact]).

### 11.2.2.2 HCRN Requirements for Reporting SAEs to Merck

HCRN will report all SAEs to Merck **within 1 business day** of receipt of the SAE Submission Form from a site. Follow-up information will be provided to Merck as it is received from site.

## 11.3 Sponsor-Investigator Responsibilities

HCRN will send a SAE summary to the sponsor-investigator **within 1 business day** of receipt of SAE Submission Form from a site. The sponsor-investigator will promptly review the SAE summary and assess for expectedness and relatedness.

## 11.4 IND Exempted Protocols

For protocols exempt from the requirements of an IND, HCRN will continue to facilitate compliance of applicable requirements for the sponsor-investigator in relation to this study. This includes but is not limited to 21 CFR 50.20 informed consent, 21 CFR Part 56 IRB, and pertinent sections of the Public Health Service Act and FDAAA.

## 11.5 IND Safety Reports Unrelated to this Trial

Merck will provide to HCRN IND safety reports from external studies that involve the study drug(s) per their guidelines. HCRN will forward safety reports to the sponsor-investigator who will review these reports and determine if revisions are needed to the protocol or consent. HCRN will forward these reports to participating sites **within 1 business day** of receiving the sponsor-investigator's review. Based on the sponsor-investigator's review, applicable changes will be made to the protocol and informed consent document (if required). Any changes made to the protocol and/or informed consent document will be submitted to the FDA by MICHR-MIAP. All IND safety reports will also be made available to sites via the EDC system.

Upon receipt from HCRN, site investigators (or designees) are responsible for submitting these safety reports to their respective IRBs, as per their IRB policies.

## 12. STATISTICAL METHODS

### 12.1 Objectives

#### 12.1.1 Primary Objective

Evaluate 6 month radiographic progression free survival (rPFS) rate with lenvatinib and pembrolizumab combination therapy in metastatic NEPC.

#### 12.1.2 Secondary Objectives

- Assess the safety of pembrolizumab and lenvatinib combination therapy in metastatic neuroendocrine prostate cancer (NEPC).
- Assess overall survival (OS).
- Assess objective response rate (ORR).
- Assess duration of response (DoR).

#### 12.1.3 Correlative / Exploratory Objectives

- Correlate genomic sequencing results with clinical outcomes in the study population.
- Correlate PDL-1 status and tumor mutation burden with clinical outcomes.
- Correlate gut microbiome data with clinical outcomes.

## 12.2 Endpoints

### 12.2.1 Definition of Primary Endpoint

rPFS is defined as the date of Cycle 1 Day 1 to date of radiologic progression of soft tissue lesions per RECIST 1.1 or death whichever occurs first. rPFS is defined as the date of Cycle 1 Day 1 to date of progression of bone lesions (non-measurable disease) per PCWG3 criteria or death whichever occurs first. Censoring of rPFS is described in Section 9.8.2.

### 12.2.2 Definition of Secondary Endpoints

- Safety of the combination will be assessed based on NCI Common Terminology Criteria for Adverse Events (CTCAE) version 5.0.
- Overall survival (OS) will be measured from Cycle 1 Day 1 to date of death from any cause. OS is further defined (including its censoring) in Section 9.8.3.
- ORR will be the proportion of patients achieving either a complete response (CR) or a partial response (PR), among all patients meeting the criteria of Section 12.6, as well as among all patients enrolled.
- DoR will be measured from the start date of the best response achieved until the date of relapse (i.e., progression). DoR is further defined (including its censoring) in Section 9.8.4. DoR applies to only the CR or PR patients.

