### 3. ELIGIBILITY CRITERIA

#### 3.1 Inclusion Criteria

Subject must meet all of the following applicable inclusion criteria to participate in this study:

1. Written informed consent and HIPAA authorization for release of personal health information prior to registration. **NOTE:** HIPAA authorization may be included in the informed consent or obtained separately.
2. Age  $\geq$  18 years at the time of consent.
3. Eastern Cooperative Oncology Group (ECOG) performance status of 0 or 1 within 7 days prior to the date of registration.
4. The subject has histologically proven prostate cancer with radiologic evidence of metastases and at least one of the following:
  - Small-cell or NEPC morphology (determined by the enrolling center) on the basis of tissue sample.
  - Prostate adenocarcinoma with IHC staining for neuroendocrine markers (e.g., chromogranin and synaptophysin).
  - Presence of visceral metastases or high volume disease ( $> 4$  sites of metastases) with a PSA  $\leq 5$ .
  - Serum chromogranin A level  $\geq 5 \times$  upper limit of normal (ULN) and/or serum neuron specific enolase (NSE)  $\geq 2 \times$  ULN.
  - RB1 deletions or mutations noted on genomic testing
  - Trans-differentiated carcinoma or poorly-differentiated carcinoma
5. Subject has adequate organ function as defined in the table below; all screening labs to be obtained within 10 days prior to Cycle 1 Day 1.
  - Absolute neutrophil count (ANC)  $\geq 1500/\text{mm}^3$  without colony stimulating factor support
  - Platelets  $\geq 100,000/\text{mm}^3$
  - Hemoglobin  $\geq 9 \text{ g/dL}$ . Transfusions are allowed as needed.
  - Serum creatinine  $\leq 1.5 \times$  ULN or creatinine clearance (CrCl)  $\geq 30 \text{ mL/min}$ . For creatinine clearance estimation, the Cockcroft and Gault equation should be used.
  - Bilirubin  $\leq 1.5 \times$  the upper limit of normal (ULN) OR direct bilirubin  $\leq$  ULN for participants with total bilirubin levels  $> 1.5 \times$  ULN. For subjects with known Gilbert's disease, bilirubin  $\leq 3.0 \text{ mg/dL}$
  - Alanine aminotransferase (ALT) and aspartate aminotransferase (AST)  $\leq 2.5 \times$  ULN if no liver involvement, or  $\leq 5 \times$  ULN with liver involvement

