#### **5. TREATMENT PLAN**

Eligible patients will be treated with the combination of lenvatinib and pembrolizumab. A cycle equals 21 days and therapy will continue until radiographic progression, intolerable toxicity, or patient/physician wishes to discontinue protocol therapy. A maximum of 35 cycles may be administered. On Day 1, when both pembrolizumab and lenvatinib are administered, patients should take the lenvatinib per their normal routine.

If measurable disease is present, response will be assessed by RECIST 1.1 criteria. For bone only metastases at least 2 new areas of metastases will qualify as progression, and PSA response will be also reported per Prostate Cancer working Group 3 guidelines. Section 7 calendar outlines the schedule for assessments.

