#### **6.4 Protocol Therapy Discontinuation**

In addition to discontinuation from therapy related to toxicities as outlined above, a subject will also be discontinued from protocol therapy and followed per protocol under the following circumstances outlined below. The reason for discontinuation of protocol therapy will be documented on the electronic case report form (eCRF)

- Completion of maximum of 35 cycles of study treatment.
- Documented disease progression per RECIST 1.1 (subjects with measurable disease) or PCWG (subjects without measurable disease). If a subject is receiving clinical benefit (as determined by treating physician), treatment can continue after discussion with sponsor-investigator.
- Site investigator determines a change of therapy would be in the best interest of the subject
- Subject requests to discontinue protocol therapy, whether due to unacceptable toxicity or for other reasons
  - In a subject decides to prematurely discontinue protocol therapy (“refuses treatment”), the subject should be asked if he or she may still be contacted for further scheduled study assessments. The outcome of that discussion should be documented in both the medical records and in the eCRF.
- If protocol therapy (both drugs) is interrupted for  $\geq 42$  days from the expected day of the next treatment. If one drug is permanently discontinued, treatment with the other drug may continue at investigator discretion.

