## **9. CRITERIA FOR DISEASE EVALUATION**

RECIST 1.1 criteria will apply to subjects with measurable disease. For patients with non-measurable disease the PCWG3 criteria will be utilized for response assessment. PSA response and progression will also be evaluated per PCWG3 criteria. [9]

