#### 9.5 Evaluation of Target Lesions

**NOTE:** In addition to the information below, also see the international criteria proposed by the Response Evaluation Criteria in Solid Tumors (RECIST) Committee, version 1.1[8] (Eur J Cancer 45;2009:228-247) for special notes on the assessment of target lesions.

Complete Response (CR)	Disappearance of all target lesions. Any pathological lymph nodes (whether target or non-target) must have reduction in short axis to <10 mm.
Partial Response (PR)	At least a 30% decrease in the sum of the diameters of target lesions, taking as reference the baseline sum diameters
Progressive Disease (PD)	At least a 20% increase in the sum of the diameters of target lesions, taking as reference the smallest sum on study (this includes the baseline sum if that is the smallest on study). In addition to the relative increase of 20%, the sum must also demonstrate an absolute increase of at least 5 mm. (Note: the appearance of one or more new lesions is also considered progressions).
Stable Disease (SD)	Neither sufficient shrinkage to qualify for PR nor sufficient increase to qualify for PD, taking as reference the smallest sum diameters while on study

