### **12.6 Assessment of Efficacy**

All patients receiving 1 cycle of study treatment (any amount of pembrolizumab and lenvatinib) and having had radiology imaging for disease assessment will be evaluable for efficacy.

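### Both ORR denominators include patients without measurable disease, for whom the protocol writes no partial response, and no ORR in measurable disease is planned

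*Combined protocol and SAP*

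**What the plan says.** **Endpoint.** Sections 2.2.2 and 12.2.2 give ORR as the proportion of patients with CR or PR, taken "among all patients meeting the criteria of Section 12.6, as well as among all patients enrolled". Section 12.4.2 analyses it like the 6-month rPFS rate, with a point estimate and a two-sided Wilson 95% CI.

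**Who is counted.** Inclusion criterion 4 opens: "The subject has histologically proven prostate cancer with radiologic evidence of metastases and at least one of the following". None of the listed features, and no other inclusion criterion, asks for a measurable lesion. Under Section 12.6, patients who received one cycle and "having had radiology imaging for disease assessment will be evaluable for efficacy". Measurable disease is not mentioned there.

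**Patients without measurable disease are expected.** Section 5 has a progression rule for bone-only metastases, and Section 6.4 has a separate discontinuation criterion for progression in subjects without measurable disease. Section 9.2 classes bone lesions as non-measurable.

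**How response is defined.**
- Section 5: "If measurable disease is present, response will be assessed by RECIST 1.1 criteria".
- Section 9: "RECIST 1.1 criteria will apply to subjects with measurable disease", and "For patients with non-measurable disease the PCWG3 criteria will be utilized for response assessment".
- Section 9.5 defines PR as "At least a 30% decrease in the sum of the diameters of target lesions, taking as reference the baseline sum diameters". Under 9.3, target lesions are chosen from measurable lesions.
- Section 9.6 gives non-target disease three categories: CR, Non-CR/Non-PD and PD.
- In Section 9.7, every row that yields PR needs a target-lesion CR or PR.

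**The concern.** A patient with bone-only or other non-measurable disease has no target lesion, so the PR written in 9.5 is out of reach. Section 9 points to PCWG3 for that patient's response but does not say what would count as CR or PR for the ORR. The patient still enters the denominator, on both planned versions, once the entry and imaging conditions are met.

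The reported ORR would then depend partly on how many enrolled patients happen to have measurable disease, and not only on how often measurable disease shrinks. Neither planned denominator separates the two. The open definition also leaves sites room to differ. Section 5 says that PSA response will be reported too, and nothing states that it stays out of the ORR.

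Section 12.4.3 also models clinical response, as defined in Section 9, on the exploratory markers, so the same ambiguity carries into those models.

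**Working it through.** **The plan's own figures.** The documents state no assumed ORR and no sample size for it. The trial size comes from the Simon design in 12.3, which reproduces: with 2/27 and 6/40, exact binomial calculation gives PET 0.4846, ASN 33.70 and power 0.9001, against the stated 0.485, 33.70 and 0.90. Enrolment is 40/(1 − 0.20) = 50. The ORR denominators are therefore about 40 (evaluable) and up to 50 (enrolled).

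**Routes to response, by type of disease**

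| | Measurable disease | Non-measurable disease only |
|---|---|---|
| PR | Written (9.5) | None written |
| CR | Written (9.5, 9.6) | Possible under 9.6, but no row in 9.7 maps it to an overall response |
| PCWG3 response | – | Invoked in Section 9; no CR or PR defined |
| In ORR denominators | Yes | Yes |

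**Formula.** Let m be the share of counted patients without measurable disease, R the ORR in measurable disease, and c the CR rate in non-measurable disease. Then

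ORR = (1 − m)R + mc, so ORR − R = −m(R − c).

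None of m, R and c is given in the documents, so the values below are assumptions, with R = 30% throughout.

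| m | c = 0 (worst case) | c = 10% |
|---|---|---|
| 10% | 0.90 × 30 = 27% | – |
| 20% | 0.80 × 30 = 24% | 24 + 0.20 × 10 = 26% |
| 30% | 0.70 × 30 = 21% | – |
| 40% | 0.60 × 30 = 18% | 18 + 0.40 × 10 = 22% |

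From the second form of the formula, there is no dilution when m = 0 or when c = R. If sites counted something other than CR as response in these patients, such as a PSA response, that rate would take the place of c. Should it exceed R, the difference would change sign.

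**In whole patients, with Wilson 95% CIs and c = 0**

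| Setting | Measurable disease | All counted |
|---|---|---|
| 50 enrolled, m = 20% | 12/40 = 30.0% (18.1–45.4%) | 12/50 = 24.0% (14.3–37.4%) |
| 40 evaluable, m = 40% | 7/24 = 29.2% (14.9–49.2%) | 7/40 = 17.5% (8.7–31.9%) |

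Interval widths in percentage points: 27.3 against 23.1 in the first setting (ratio 1.18), and 34.3 against 23.2 in the second (ratio 1.48).

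**The case against.** **Section 9 assigns these patients to PCWG3, so the RECIST tables do not show that they cannot respond.** This stands. A reader might infer that such patients can never respond and that the ORR is structurally biased downwards. The documents do not go that far. They refer response in non-measurable disease to a source outside the text and do not say how it feeds the ORR. What can be shown is that no PR is written for them and that the assigned criteria are left undefined for this endpoint.

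**ORR is CR plus PR, and 9.6 describes a CR for non-target disease.** This also stands. Patients without measurable disease are not non-responders by definition, and the c = 0 figures are a worst case. Dilution remains whenever m is above zero and c is below R.

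**The size has no anchor.** Correct. If every enrolled patient has measurable disease, nothing changes.

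**A response rate over all treated or enrolled patients is a valid, conservative quantity.** Agreed, and it is prespecified. This is a reason to keep both planned denominators. It does not supply the missing rate in patients assessable by RECIST.

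**No decision hangs on ORR.** Correct. The hypothesis in 1.5 and the rule in 12.3 concern 6-month rPFS only. A reader might also infer that the planned ORR cannot be set beside the response rates in Section 1.1 (48% with front-line platinum–etoposide, 18.7% with pembrolizumab in small cell lung cancer). The documents do not say whether those denominators were limited to measurable disease, and the settings differ anyway, so that argument is not relied on here.

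**Conclusion.** The point holds as a gap in the definition and reporting of a secondary endpoint. The protocol admits patients without measurable disease, writes no PR for them, leaves their PCWG3 response undefined, counts them in both ORR denominators, and plans no ORR in measurable disease.

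The likely effect is dilution by m(R − c). At an assumed R of 30%, that is 3 to 12 percentage points for m from 10% to 40% if c = 0. If c = 10%, it is 4 points at m = 20% and 8 points at m = 40%. It is nil if m = 0 or c = R. A firm claim of downward bias is not supported, because the direction depends on what is counted as response in non-measurable disease. The primary analysis is not affected. The change is worth making because it is cheap and yields a rate that the plan as written would not report.

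**What to change.** 1. In Sections 2.2.2 and 12.2.2, add ORR among patients with at least one target lesion at baseline as the main ORR, with a Wilson 95% CI. Keep the two planned denominators as supplementary.
2. State in the same sections that PSA response does not count towards ORR and is reported separately.
3. Add a row or short block to Section 9.7 for patients with non-target disease only, built on the categories already in 9.6, and say in Section 9 how the PCWG3 assessment relates to the ORR.

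**Cost.** A few sentences and one extra table row. Section 9.3 already requires target lesions to be recorded at baseline, so no new data are needed. The statistical downside is a wider interval from the smaller denominator. It is modest if 20% lack measurable disease, but not slight if 40% do: 14.9–49.2% for 7/24 against 8.7–31.9% for 7/40.
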